H1a: FV acquisition, consumption, and diet quality will increase in the control group featuring a reduction in the effective price of fresh FV and

H1b: Food waste will increase in the control group featuring a reduction in the effective price of fresh FV,

where the effective price of fresh FV is reduced via free FV provision (the pick-up site is centrally located with free parking and convenient for most Baton Rouge area residents). According to Hamilton and Richards (Proposition 1) if food waste reduction knowledge (θ) is increased then the amount of fresh food consumed will increase while the amount wasted will decline so long as $F > 1 - \gamma$, i.e., so long as demand for fresh food is not too price elastic. Hence, we forward:

H2a: FV acquisition will increase in the treatment group featuring both a reduction in the effective price of fresh FV and a smart intervention to reduce food waste,

H2b: FV consumption will increase without increasing total energy intake and diet quality will also increase in relation to the control group, and

H2c: Food waste in the treatment group will be less than food waste in the control group.

Expected Outcomes

We expect to assess whether programs that subsidized FV acquisition are efficiently translating program dollars into improved nutrition rather than into increased energy intake and increased FV waste and to develop interventions that ensure funds targeted

to increase household FV acquisition are efficiently translated into improved household nutrition. We will:

1. Assess the impact of free FV provision on FV intake and household food waste production
2. Measure the efficacy of the smart intervention
3. Provide insights to guide future policies and interventions that target increased FV consumption through free or subsidized FV provision.

We also expect to improve upon the efficiency of the FoodImage app through continual assessment of participant feedback and by improving the efficiency of image analysis and data input.

Study Endpoints

Primary analysis objectives follow the hypotheses, which we are sufficiently powered to assess:

- 1) Quantify baseline distributions:
 - a. Mass (g), energy (kcal), and macronutrients (g and kcal) for household food waste levels, food purchasing patterns, food intake, and consumption of FV including beginning FV inventory, total FV acquisition, and total FV intake

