 - b. FPED values, i.e. serving size, for food intake and consumption of FV including FV inventory, total FV acquisition, and total FV intake
 - c. Quantify baseline diet quality (i.e. food intake as assessed by the HEI)
- 2) Determine how the smart intervention altered:
 - a. Mass (grams), energy (kcal), and macronutrients (g and kcal) for household food waste levels, food purchasing patterns, food intake, and consumption of FV including FV inventory, total FV acquisition, and total FV intake
 - b. FPED values, i.e. serving size, for food intake and consumption of FV including FV inventory, total FV acquisition, and total FV intake
 - c. Quantify diet quality (i.e. food intake as assessed by the HEI)
 - d. Acquisition and intake of non-FV foods
 - e. The percent of household food waste that was FV

Secondary analysis objectives include assessing the demographic (e.g., age, education), household (SNAP eligibility, household size, beginning food inventories), and attitudinal factors (e.g., frugality, health and environmental consciousness) related to the primary analysis targets.

Power analysis

Power analysis was conducted for change in the primary outcome variable (grams [g] of food waste) from baseline to the end of the intervention to detect significant differences between treatment and control groups. Following the methods of our previous study, waste data will be summarized and analyzed by aggregating across measurement days. Based on weekly data from our previous study, the participants in the group receiving a smart food waste reduction intervention reduced their waste at meals by 331 g while the control group only reduced their waste by 33 g (298 g group difference), while the pooled standard deviation of the change in food waste between the control and treatment groups was 295 g, yielding an effect size of 1.01. The power to detect an effect size of 1.01 is 0.92 if there is no attrition (23 per group) and is 0.88 if attrition exceeds the 10% expectation (20 per group or 13% attrition). Given the power analysis is based upon an RCT that did not involve the provision of free FV, we expect effect sizes to be larger in the proposed study due to the presence of free FV, yielding even higher power than projected above.

Provisions to Monitor the Data to Ensure the Safety of Subjects

Adverse events will be monitored at each intervention visit. The PI and his co-investigators will review all data continuously to ensure the safety of each subject.

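### Study Endpoints claims adequate power for all the hypotheses, but power was computed only for between-group change in grams of food waste (H2c), and no alpha or multiplicity rule is stated

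*Combined protocol and SAP*

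**What the plan says.** Two adjacent sections of the combined protocol and SAP give different accounts of what is primary and what is powered.

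- **Study Endpoints** opens with "Primary analysis objectives follow the hypotheses, which we are sufficiently powered to assess". Objective 1 describes baseline distributions. Objective 2 asks how the intervention altered mass, energy and macronutrients of household waste, and also "food purchasing patterns, food intake, and consumption of FV including FV inventory, total FV acquisition, and total FV intake". It adds FPED values, HEI, non-FV foods and the FV share of waste. The secondary objectives are confined to demographic, household and attitudinal correlates, so no outcome measure is placed in a lower tier there.
- **Power analysis** begins "Power analysis was conducted for change in the primary outcome variable (grams [g] of food waste", in the singular, and deals with the treatment-control difference in change from baseline. That is H2c.
- **Theory Driven Hypotheses** lists H1a and H1b (increases within the control group), H2a (an increase in FV acquisition in the treatment group), H2b (FV consumption, energy intake and diet quality) and H2c. Under Objectives, H1 is to be tested by comparing baseline with follow-up in the control arm alone.

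The documents state no alpha, sidedness, test or model for any outcome, no multiplicity adjustment and no testing order.

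**The concern.** A claim of adequate power that covers five hypotheses rests on a calculation for one. H1a and H1b use 20 to 23 people in a single arm, and neither they nor H2a and H2b have an effect size or SD in the plan. The borrowed effect is a between-group difference in food waste under an earlier waste-reduction intervention. It says nothing about HEI, FV acquisition or energy intake. It gives no support for H1b either, because waste in that study's control group fell by 33 g, whereas H1b predicts a rise.

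Two errors of interpretation become possible. A null result on H1 or H2b could be read as an adequately powered negative. A positive result on one of many outcomes labelled primary could be reported with no agreed error rate behind it. The plan says its results should guide policy on free or subsidised FV provision, so both matter.

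**Working it through.** **1. Reproduce the stated power.** Inputs, all from Power analysis: "298 g group difference" (331 − 33 = 298) and "pooled standard deviation of the change in food waste between the control and treatment groups was 295 g", "yielding an effect size of 1.01".

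d = 298/295 = 1.01.

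Two-sample t test, two-sided alpha 0.05, noncentrality d × √(n/2), df = 2n − 2:

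- n = 23: noncentrality 1.01 × √11.5 = 3.43, power 0.918. The plan says "The power to detect an effect size of 1.01 is 0.92 if there is no attrition (23 per group").
- n = 20: noncentrality 1.01 × √10 = 3.19, power 0.875. The plan says it "is 0.88 if attrition exceeds the 10% expectation (20 per group or 13% attrition").

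The figures reproduce. One-sided 0.05 gives 0.958 and 0.932; two-sided 0.025 gives 0.861 and 0.801. Neither matches, so two-sided 0.05 is inferred for this contrast. It is an assumption for everything below.

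**2. What the same sample size can detect elsewhere.** The within-arm test is a one-sample t on change, with noncentrality d × √n and df = n − 1.

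| | n = 23 | n = 20 |
|---|---|---|
| Between-group d for 80% power | 0.84 | 0.91 |
| Within-arm standardised change for 80% power | 0.61 | 0.66 |
| Between-group power at an assumed d = 0.5 | 0.38 | 0.34 |
| Within-arm power at an assumed d = 0.5 | 0.63 | 0.56 |

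The thresholds convert to grams for H1b only, and only if the 295 g SD for change in meal waste also holds within the control arm: 0.61 × 295 = 180 g and 0.66 × 295 = 195 g. H1a, H2a and H2b have no SD in the plan, so no such conversion is possible.

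**3. How many outcomes objective 2 contains.** The plan gives no count. Two readings:

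- By category: 3 measures × 4 domains = 12, plus FPED 2, HEI 1, non-FV foods 2, FV share of waste 1. Total 18.
- Expanded: 8 measures (mass, energy, and three macronutrients each in g and kcal, the three being an assumption) × 6 targets = 48, plus FPED 4, HEI 1, non-FV 2, FV share 1. Total 56.

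Objective 1 is descriptive and adds no type I error.

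**4. Family-wise error if each were tested at 5% with all nulls true.** Independent tests: 1 − 0.95^k. Correlated tests: simulation with equicorrelated normal statistics.

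| Correlation | k = 18 | k = 56 |
|---|---|---|
| 0 | 0.60 | 0.94 |
| 0.3 | 0.51 | 0.83 |
| 0.5 | 0.40 | 0.65 |
| 0.7 | 0.28 | 0.42 |

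**5. Effect of correcting by Bonferroni.** Power at d = 1.01 with 23 and 20 per group:

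- 5 hypotheses (alpha 0.01): 0.76 and 0.68.
- 18 outcomes (alpha 0.0028): 0.60 and 0.51.
- 56 outcomes (alpha 0.0009): 0.46 and 0.36.
- Grams of waste as sole primary at 0.05: 0.92 and 0.88, as the plan states.

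**The case against.** The best defence is that the Power analysis section already names one primary outcome, so this is inconsistent labelling and not a trial with dozens of primary endpoints. That is largely right, and it is why the repair is small. It does not rescue the sentence in Study Endpoints, which extends the power claim to the hypotheses as a whole.

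Three stronger readings are tempting, and the documents do not support them:

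- *That every outcome is to be tested at the full 5%.* No alpha or test is given for any outcome. The defect is that error control is unspecified. Nor does the plan say that any single significant result would count as a primary success.
- *That the power claim is false.* It reproduces for H2c. For the other hypotheses it is unsupported: without their effect sizes and SDs it can be neither confirmed nor refuted.
- *That false positives are nearly certain.* A family-wise error of 0.95 needs about 59 independent tests with every null true. These outcomes are grams, kilocalories and macronutrients of the same food, so they are correlated.

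The upper count can also be disputed. If macronutrient kilocalories are a fixed multiple of grams, the two give the same test, and the 48 combinations in 2a become 5 × 6 = 30. The family-wise error for those is 0.79 if independent and about 0.34 to 0.66 at correlations of 0.7 to 0.3. The Objectives section also labels some energy-intake and food-replacement analyses exploratory, so outcomes are partly tiered already. Both points narrow the size. Neither supplies a power basis or a testing rule.

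Lastly, H1 is one of the trial's two specific objectives, and removing it would change the trial. That stands: H1 should remain a stated objective, without a confirmatory power claim.

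**Conclusion.** The point holds in this form: Study Endpoints and Power analysis conflict on what is primary, and the claim of sufficient power is supported for H2c only. H1a, H1b, H2a and H2b have no power basis. At two-sided 0.05 (assumed) and 20 to 23 per group, they reach 80% power only for within-arm changes of about 0.61 to 0.66 SD or between-group effects of about 0.84 to 0.91 SD.

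The multiplicity figures (0.28 to 0.60 for 18 outcomes, 0.42 to 0.94 for 56) are conditional. They rest on testing each outcome at 5%, all nulls being true, equal correlation between 0 and 0.7, and a count the plan does not give. Even the lowest is more than five times the nominal 5%. The stated power for grams of waste is not in question here.

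**What to change.** In Study Endpoints:

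1. Name change in grams of household food waste, treatment versus control, as the sole primary outcome at two-sided 0.05, in line with Power analysis.
2. Replace the general power claim with a statement that power was computed for H2c only.
3. Keep H1a, H1b, H2a, H2b and the remaining objective-2 outcomes as stated objectives, but report them as secondary with 95% confidence intervals and no confirmatory claim. Alternatively, test them in a prespecified order after H2c succeeds.
4. Leave objective 1 as descriptive.

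This needs no added participants or data, and power for H2c stays at 0.92 and 0.88. The cost is that fewer outcomes can be called confirmatory. This falls mainly on H1, which would be reported as an estimate with its precision.

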Protocol Title: USING THE FOODIMAGE™ APP TO ASSESS SMART INTERVENTIONS DESIGNED TO IMPROVE NUTRITION & REDUCE FOOD WASTE

PI Name: [name].; [name].; Pennington Biomedical Research Center

Co-Investigators: [name]., PI of the parent award at Ohio State University
[name]., Louisiana State University (LSU)
[name], Ph. D., Pennington Biomedical Research Center

Protocol Version Date: 10/27/2021

IRB Review History

This is a subcontract project with Ohio State University as the lead institution and Pennington Biomedical Research Center (PBRC), part of the Louisiana State University system, as the subcontractor who will conduct the human subjects research. PBRC will pursue the research outlined herein and share the resulting data with [name] at OSU and [name] at LSU.

Objectives

Long-term Goals and Specific Objectives

Our *long-term goal* is to simultaneously improve global sustainability, enhance national food security, and improve U.S. productivity through improved nutritional intake while improving the competitiveness of the U.S. food system by reducing U.S. household food waste. To reduce household food waste and improve individual nutrition, we leverage the FoodImage™ smartphone app ¹, a novel method for measuring household food acquisition, food intake, and food waste decisions, to assess the efficacy of a smart intervention that targets food waste reduction and diet quality improvement. The intervention is designed to improve nutrition by offsetting intake of less nutritious foods with increased fresh fruit and vegetable (FV) intake while simultaneously reducing household food waste via strategies tailored to participating households.

Specific objectives include using the FoodImage app in a randomized controlled trial (RCT), in which we will use the data collected to:

Enroll and Baseline Data Collection	N=46	
Randomly Assign within Matched Pairs	Control (N=23)	Treatment (N=23)
Info on Benefits of FV Consumption	No	Yes
Provision of Free FV Box	Yes	Yes
Intervention	Stress Management	Food Waste Reduction + Replace Less Healthy Foods with FV

We will use the data collected to:

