Data from the FoodImage app will be prepared for analysis using methods detailed in [name] et al. (2020)¹. Briefly, images captured through the app are viewed by PBRC's nutrition staff who identify nutrient matches using Standard Reference (SR) 28 and the Food and Nutrient Database for Dietary Studies (FNDDS) 6.0¹⁴ (USDA 2020b)¹⁵ and estimate the mass of portions of food acquired, prepared, selected, consumed, returned, and discarded at each stage. Specifically, we will obtain mass (grams), energy (kilocalories), and macronutrients for shop, prep, eat, and toss occasions. The SR database provides inedible percentages. Furthermore, for all foods except raw meats where the SR database is used, we will obtain highly granular data. The FNDDS database translates whole food items into FPED values which converts each consumed food and beverage into the 37 USDA Food Patterns components¹⁶. The FPED values are used to assist in the quantification of diet quality (HEI) and to guide healthy food intake patterns (e.g., the 'five a day' campaign to promote FV consumption). The Food Patterns are measured as cup equivalents for fruits and vegetables. Thus, we can examine the number of servings of fruits, vegetables, dairy, grains, and proteins (each of the food groups) consumed. Also, we will examine diet quality in relation to the USDA Dietary Guidelines for Americans with the HEI¹⁷. During the two ≥ 3 -day intensive collection windows, participants record the source, reason and destination of all food waste on the app, which is attached to each data point. Receipts associated with food acquisition, which are collected for all 28 days, are processed via Optical Character Reader (OCR) with resulting price data checked for accuracy by human raters.

The method proposed by Pocock and Simon¹⁸ will be used for intervention assignment to minimize imbalance among factors that might be associated with outcomes of interest. Specifically, randomization will be adaptive according to the values of the Aitchison distance calculated using the following prioritized drivers of FV consumption and food waste: 1) the presence of children in the home vs. no children, 2) SNAP eligibility vs. being ineligible, and 3) the presence of a fruit tree and or garden at the home vs. the absence of these amenities. Greevy et al.¹⁹ the sample size required for achieving the same power is often reduced if factors associated with the outcomes are balanced among the intervention groups.

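### The primary model is not named, and the stated basis for the primary outcome leaves out baseline waste and the three balancing factors, while allocation is described in two conflicting ways

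*Combined protocol and SAP*

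**What the plan says.** **Primary outcome.** The Power analysis section states: "Power analysis was conducted for change in the primary outcome variable (grams [g] of food waste) from baseline to the end of the intervention". Its inputs come from a previous study in which the intervention group "reduced their waste at meals by 331 g while the control group only reduced their waste by 33 g (298 g group difference"), and "the pooled standard deviation of the change in food waste between the control and treatment groups was 295 g". It mentions no covariate, alpha or sidedness. The only other statement there on analysing waste is that it will be aggregated across measurement days, following the previous study's methods. Objective 2 speaks of post-intervention waste compared with control, and H2c (Theory Driven Hypotheses) of waste in one group being less than in the other. Neither mentions change.

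**Data available.** Under Procedures, baseline waste is recorded in the week before Visit 2, where randomisation takes place. The Analysis section lists three balancing factors, each a yes/no contrast: children in the home, SNAP eligibility, and a fruit tree or garden. SNAP eligibility returns only among the secondary analysis objectives, as a factor related to the outcomes.

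**Allocation.** The table under Objectives reads "Randomly Assign within Matched Pairs". The Analysis section names the Pocock and Simon method and adds that "randomization will be adaptive according to the values of the Aitchison distance calculated using the following prioritized drivers". It supports balancing with the argument that "the sample size required for achieving the same power is often reduced if factors associated with the outcomes are balanced among the intervention groups".

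**The concern.** Three gaps meet in the same comparison.

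- **The model is open.** Change, follow-up level and a paired analysis are all compatible with some part of the text. With about 20 completers per group they can give different answers, and nothing stops the choice being made after the data are seen.
- **Precision may be left unused.** A raw change score is generally less precise than adjustment for baseline. Balancing on prognostic factors and then ignoring them leaves the standard error too large, so the test is conservative. The protocol cites the efficiency of balancing but states no analysis that would collect it in full.
- **The allocation system cannot be built from the text.** Randomising within pairs and sequential minimisation are different designs, and each calls for an analysis that reflects it. The Analysis section also does not say how an Aitchison distance, which is built on log-ratios, is to be applied to yes/no factors.

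**Working it through.** **1. Reproduce the stated power.** Inputs from the Power analysis section: difference 331 − 33 = 298 g; SD of change 295 g; d = 298/295 = 1.01; 23 or 20 per group. Alpha is not stated; 0.05 two-sided is assumed. A two-sample t-test (noncentral t, noncentrality d√(n/2)) gives:

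| n per group | Protocol | Recomputed, two-sided 0.05 | Recomputed, one-sided 0.05 |
|---|---|---|---|
| 23 | 0.92 | 0.918 | 0.958 |
| 20 | 0.88 | 0.875 | 0.932 |

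The protocol's figures are those of an unadjusted two-sided t-test on change.

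**2. Change score against baseline adjustment.** Let s be the baseline SD, ks the follow-up SD and ρ the correlation between the two periods.

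- Change score: variance s²(1 + k² − 2ρk)
- ANCOVA: variance k²s²(1 − ρ²)
- Difference: s²(1 − ρk)², which is never negative

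Apart from the few degrees of freedom spent, ANCOVA is therefore never less precise. With equal SDs (k = 1) the ratio of the variances is (1 + ρ)/2.

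**3. Size of the gain.** The documents give neither ρ nor k, so both are assumed. The 295 g SD of change is held fixed, the adjusted SD is 295 × √ratio, and four degrees of freedom are spent (baseline plus three factors). The factors themselves are credited with no explanatory value. Power is for 20 per group, against 0.875 unadjusted.

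| k | ρ | Change variance / s² | ANCOVA variance / s² | Ratio | Variance reduction | Power |
|---|---|---|---|---|---|---|
| 1.0 | 0.3 | 1.40 | 0.91 | 0.65 | 35% | 0.97 |
| 1.0 | 0.5 | 1.00 | 0.75 | 0.75 | 25% | 0.95 |
| 1.0 | 0.7 | 0.60 | 0.51 | 0.85 | 15% | 0.92 |
| 1.3 | 0.3 | 1.91 | 1.54 | 0.81 | 19% | 0.93 |
| 1.3 | 0.5 | 1.39 | 1.27 | 0.91 | 9% | 0.90 |
| 1.3 | 0.7 | 0.87 | 0.86 | 0.99 | 1% | 0.88 |

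**4. Balancing and then ignoring the factors.** This was simulated with 20 per group and a perfectly balanced factor that explains an assumed share of outcome variance. The unadjusted t-test at nominal 0.05 has type I error of about 0.04 if the share is 10% and about 0.028 if it is 20%. At d = 1.01 and a 20% share its power is about 0.90, against 0.88 with no such factor. Balance thus helps a little even without adjustment, but the test falls short of its nominal level.

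**5. If pairs are real.** A paired analysis of 23 pairs (22 degrees of freedom) has power 0.905 with no within-pair correlation and 0.955 with an assumed 0.2. Which design is used therefore changes both the analysis and its power.

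**The case against.** **The quoted sentence is about power, not the model.** This stands. A reader might infer that the primary analysis is an unadjusted change score. No section says so, and an unadjusted power calculation is compatible with an adjusted analysis. The finding is that the model is unnamed and its only quantified basis is unadjusted.

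**The stated power is adequate.** This also stands. A reader might infer an underpowered trial, but on the protocol's own inputs power is 0.88 to 0.92, and a change-score comparison remains valid under randomisation. Those absolute figures do rest on an SD for weekly waste at meals carrying over to household waste recorded over about three days.

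**The gain depends on equal SDs.** This stands in part. Free produce arrives between the two periods and H1b expects control waste to rise, so follow-up may be the more variable period. At 1.3 times the baseline SD and ρ = 0.7 the gain almost vanishes. It does not become a loss beyond the few degrees of freedom.

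**Balancing helps without adjustment.** True, as step 4 shows. It is too strong to say that the saving appears only in an adjusted analysis. The documents do not show how strongly the three factors predict waste.

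**The allocation conflict is narrower than it looks.** The Aitchison distance can be read as the balance metric within the Pocock and Simon method, not a rival scheme. A reader might conclude that the distance is undefined here because log 0 arises, but the text does not say it is applied to raw yes/no values, so it only needs defining. Nor do the documents show that pairs cannot be formed: boxes are procured on one day each week with visits ideally on the next, so several households could reach Visit 2 together. The conflict between pairs and sequential minimisation remains.

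**Conclusion.** The point holds as one of specification and efficiency. The protocol names no primary model, describes the primary comparison as change in one place and as a level in others, and uses neither baseline waste nor the balancing factors in any stated primary analysis. The matched-pair and minimisation descriptions conflict, and no analysis reflects either.

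At d = 1.01 and 20 per group, baseline adjustment raises power from 0.875 to between 0.97 and 0.92, for assumed correlations of 0.3 to 0.7 and equal SDs. With a follow-up SD 1.3 times baseline the range is 0.93 to 0.88. An unadjusted test after balancing errs on the conservative side, so false-positive risk is not inflated. The correlation, the SD ratio, the prognostic strength of the factors and two-sided 0.05 are all assumptions.

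**What to change.** 1. State the primary analysis as ANCOVA of follow-up household food waste (g) on group, with baseline waste, children in the home, SNAP eligibility and fruit tree or garden as covariates, at a stated two-sided alpha. Align the wording of Objective 2, H2c and the Power analysis section with it.
2. Reconcile the Objectives table and the Analysis section to one allocation method. If minimisation is used, define the balance metric for binary factors and state the random element. If pairs are really used, say how they are formed and make the primary analysis reflect them.

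The cost is protocol wording and four model degrees of freedom, which lower power by about 0.1 point beyond adjustment for baseline alone. No new data or participants are needed.
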